### *2.3 Study visits postpartum*

Cord blood will be sampled and stored (at  $-80^{\circ}\text{C}$ ) immediately after delivery (VPP0). A postpartum examination will be scheduled within 48 hours after delivery (VPP1) for assessment of neonatal parameters and maternal HbA1c and glycosylated fibronectin, hsCRP, proBNP, Troponin T, (12 ml, non-fasting state), as well as between **8 weeks and 12 months** after delivery (VPP2) in all patients for a detailed re-examination of glucose homeostasis at postpartum (including lifestyle and dietary pattern as well as HbA1c, glycosylated Fibronectin, hsCRP, proBNP, Troponin T, as well as a blinded CGM for 10 days and an OGTT to assess the presence of prediabetic conditions after pregnancy with GDM). The postpartum OGTT is further used to provide estimates of insulin sensitivity,  $\beta$ -cell function and hepatic insulin extraction, the major physiological components of impaired glucose tolerance.

### *2.4. Randomisation*

Participants will be randomized to either treatment (rt-CGM augmented glucose monitoring) or control group (routine care SMBG) in a 1:1 ratio. The minimisation method with a 0.85 assignment probability will be used to minimize the imbalance between the groups according to week of gestation at study entry i.e. at V1 (three strata: 24+0 to 25+6, 26+0 to 27+6, 28+0 to 29+6, 30+0 to 31+6), previous pregnancy with GDM (two strata: yes or no) and preconceptional overweight/obesity status with three strata: i. normal weight (i.e. BMI below  $25.0 \text{ kg/m}^2$ ); ii. overweight ( $\text{BMI } 25.0 - 29.9 \text{ kg/m}^2$ ); iii. obesity ( $\text{BMI equal or above } 30.0 \text{ kg/m}^2$ ). Randomisation will be performed at the second study visit (V2) by using the "MUW Randomizer" software.

## *2.5. Intervention*

Patients randomized to the intervention group will be equipped with a rt-CGM sensor (Dexcom G6 sensor, a small flexible device that records interstitial glucose levels every five minutes) at V2. The sensor will be inserted into the subcutaneous tissue of the anterior abdomen wall (if this location is not tolerated by the pregnant patients, the upper buttock or posterior upper arm may be used instead). Additionally, patients will be advised to record capillary blood glucose values if glucose alerts or readings do not match with symptoms or expectations. Participants will be educated how to exchange the sensor (has to be exchanged every ten days) and will be equipped with a real-time CGM monitor and instructed in its use. The monitor provides the user with information about current glucose levels and notifies the patient before she reaches her upper or lower glucose threshold and when glucose levels change rapidly. All patients in the intervention group will specifically trained how to use the system. As an alternative to the real-time monitor the patients' smart phone with an anonymized access to the CLARITY® mobile app can be used (details see below: "Intervention: Device description").

### *2.5.1. Intervention: Device description*

The Dexcom G6 intended use is for the management of diabetes in persons aged 2 years and older. The Dexcom G6 System is intended to replace fingerstick blood glucose testing for diabetes treatment decisions. Interpretation of the Dexcom G6 System results should be based on the glucose trends and several sequential readings over time. The Dexcom G6 System also aids in the detection of episodes of hyperglycemia and hypoglycemia, facilitating both acute and long-term therapy adjustments. The Dexcom G6 System can be used alone or in conjunction with these digitally connected medical devices for the purpose of managing diabetes.

The system consists of a sensor, transmitter, receiver, and mobile app. The sensor is a small, flexible wire inserted into subcutaneous tissue where it converts glucose into electrical current. The sensor incorporates an interferent layer that minimizes the effect of potential electroactive interferents, such as acetaminophen, by preventing it from reaching the sensor wire surface. The benefit of this interferent layer in blocking the effects of acetaminophen prevents falsely high glucose readings. Thus, users may ingest acetaminophen while wearing the G6 CGM system. The transmitter, which is connected to the sensor and worn on the body, samples the electrical current produced by the sensor and converts the measurement into a glucose reading using an onboard algorithm. The receiver and/or the app displays the glucose reading along with a rate of change arrow and a trend graph. Additionally, the receiver and/or app issues alarms and alerts to notify the patient of glucose level changes and other important system conditions. The app provides the additional capability to share data with "followers"

using the Dexcom Share service. The receiver can be put into a blinded mode using CLARITY® software. In this mode, users are unable to see the CGM data or receive CGM alerts.

CGM Ancillary Devices Dexcom CLARITY® is an accessory to users of the Dexcom CGM system. It is a software program that allows the transfer of glucose data from the CGM system to Dexcom remote servers for data management to allow use of the CGM data by the user and study clinicians. Target ranges of 60 to 140 mg/dl [3.3 to 7.8 mmol/l] will be set and the patients will be introduced in the use of alarm settings. Both participants and study sites will use CLARITY® to transfer glucose data between user and study site, whether CGM is used in blinded or real-time mode. A CLARITY® mobile app can be used for retrospective review of glucose data on the smart device and can also be set up to allow receipt of push notifications of CGM data facilitating weekly data review. For all patients (intervention and control group) an anonymized CLARITY® account will be created by using a sequential study number which is allocated at randomization (sex will be female and birth date for each account will be set to 1.1.1990 for all accounts).

### *2.5.2 Intervention: Study proceedings*

1. For participants that have a supported phone, the G6 CGM app will be installed on participant's smart phone.
2. An anonymized CLARITY® mobile account will be set up and linked to the research site.
3. Participants will use CGM data for their diabetes management.
5. A high alert threshold will be set at 140 mg/dl [7.8 mmol/l]. Low alert threshold and urgent low soon alerts will be turned off. If participants require insulin, the low alert will be turned on and the threshold set at 65 mg/dl [3.6 mmol/l]. In addition, the urgent low alert (55 mg/dl [3.1 mmol/l]), the urgent low soon alert (when glucose levels are falling fast and will be below 55 mg/dl [3.1 mmol/l] in less than 20 min) as well as alerts for rise and fall rate (3 mg/dl [0.17 mmol/l]) in addition to alerts for signal loss and no readings for more than 20 min will be enabled.
6. Participants with applicable smart phones may have CLARITY® push notifications on the CLARITY® mobile app about weekly time in range comparison enabled during the study.
7. For app users, the "Share and Follow" functionality will be discussed and encouraged (i.e. the study participants are able to invite followers to review their glucose levels).
8. For participants using the receiver only, the receiver will be downloaded into the CLARITY® clinic account at each visit.
9. For participants using real-time CGM data summary will be downloaded for documentation at V3 and V4 (between 36+0 and 38+6) as well as after delivery (VPP1)
10. The research team will review the CGM in CLARITY® to inform lifestyle and therapy recommendations.

11. The Dexcom G6 system will not be calibrated during the study period.

### *2.5. Control group*

The control group participants will perform self-monitored blood glucose testing with a study-provided blood glucose meter, including testing supplies. They will perform capillary blood glucose monitoring as routinely used for patients with GDM, i.e., at least four capillary blood glucose values daily including measurements at fasting as well as 1h after starting each meal by using a routinely available blood glucose measurement device. The study participants will keep a log book of their glucose values, which will be reviewed by clinicians from the study team at each visit and used for lifestyle and dietary recommendations as is routinely done in clinical practice. From V2 to V3 as well as once for ten days between 36+0 and 38+6 the control group receive blinded CGM; neither patients nor the treating medical staff will have access to the data recorded by the CGM sensor at this point in time. Instead, patients will control blood glucose levels based on SMBG, as is the routine procedure in current GDM treatment. Otherwise, the control group will receive the same study assessments as the intervention group. The blinded CGM will be removed and returned to Dexcom after the 10 day wear period after CGM data is uploaded to CLARITY® by an unblinded investigator who must not communicate about the results with patients or medical staff.

Each participant in the control group will be assigned a study blood glucose meter to measure and store their blood glucose values during the study. Therefore, the Contour® Next One system will be used. The meter has CE Mark clearance and is commercially available in Europe. Participants will receive an ample supply of meter test materials based on quantities routinely used. A commercially available desk-top software (Diabass® Pro), used in conjunction with Contour® Next One system glucose meter for blood glucose monitoring, will be utilized for downloading the meter data by the sites at V3 and V4 after checking that dates and times are correct.

Blood glucose meters used by the control group will be assessed to establish frequency of testing (overall and per week) as well as percentage of days with lower than four measurements per day.

### *2.6. Analyses of CGM data*

CGM data allows a detailed examination of the percentage of time in which glucose levels are in target range (65 to 140 mg/dl [3.6 to 7.8 mmol/l]), hyperglycaemic episodes (glucose  $\geq$ 140 mg/dl [7.8 mmol/l]) as well as mild ( $<65$  mg/dl [3.6 mmol/l]), moderate ( $\leq 54$  mg/dl [3.0 mmol/l]) or severe hypoglycaemic episodes (requiring third party assistance) and their duration. To this purpose, several indices of the glucose control quality will be calculated, such as GRADE (Glycaemic Risk Assessment Diabetes Equation), some indices of hypoglycaemia and

hyperglycaemia, and indices assessing the risk associated to both low and high glycaemic values, such as IGC (Index of Glycaemic Control) and ADRR (Average Daily Risk Range). Glycaemic variability will be also assessed, which can be quantified by standard deviation of the CGM data, or by more sophisticated indices, such as MAGE (Mean Amplitude Glucose Excursions), CONGA (Continuous Overlapping Net Glycaemic Action), Lability Index, as well as further indices that we developed internally, such as the Shape Index. These will be compared between real-time CGM users and controls (i.e. from data obtained during the blinded CGM wear).

## *2.7. Assessment of dietary patterns*

Dietary patterns will be assessed in all patients at V1, VPP1, and VPP2 via a published and validated Food-Frequency-Questionnaire (FFQ) proposed by the German Robert Koch Institute. It was also previously used for the German DEGS project ([www.degs-studie.de](http://www.degs-studie.de)). Information from the FFQ will be analyzed quantitatively or summarized by eating scores proposed in the literature (such as the Healthy Eating Index 2010 or Alternate Healthy Eating Index 2010) reflecting diet quality based on actual guidelines. In addition, all patients will be advised to conduct a nutritional protocol (seven days) from V2 to V3 as well as once at V4 (between 36+0 and 38+6 weeks of gestation). In a subgroup (only study site Vienna) dietary intake will also be assessed by performing 24-h-recalls by trained interviewers at V2, V4 and postpartum (VPP2): one face-to-face interview (approx. one hour) and the others as telephone interviews (approx. 30 minutes) during which data are entered simultaneously in GloboDiet. GloboDiet is a computerized program which was developed by the International Agency for Cancer Research (IARC) within the framework of the European Prospective Investigation into Cancer and Nutrition Study (EPIC-Study) for the conduction of harmonized and standardized 24-h-recalls. This open-ended software was used in numerous previous studies and was validated within the EFCOVAL project. In brief, GloboDiet is an interview-based dietary assessment instrument that allows obtaining a very detailed description and quantification of foods, recipes, and supplements consumed in the course of the preceding day and thus standardising data within and between countries. Probing questions and entering consumed foods in chronological order support the respondent's memory. The standardized structure prescribes – on the food group level – possibilities of description and quantification of food items to choose from. Quantification of consumed foods is supported by the GloboDiet picture book that comprises coloured photographs of foods in different portion sizes, photographs of familiar household measures and schematic displays of forms (e.g. bread, cake). The software provides an automatic coding of food items and recipe ingredients as well as a rough calculation of nutrient intake meant for quality control of the interview. GloboDiet is characterised by the obtained standardization of dietary data within Europe, a large number of

available foods and recipes, and a very detailed description of consumed foods. Currently, GloboDiet is one of the few dietary instruments providing comparable nutritional data within Europe. After finalisation of the interviews, GloboDiet will be linked to the local nutrition database – the Bundeslebenmittelsschlüssel (BLS) enhanced by the Austrian Nutrition Table (Österreichische Nährwerttabelle, ÖNWT), containing typical Austrian foods and recipes – allowing analyses on food ingredients level and to conduct risk assessment.

#### *2.8. Assessment of physical activity*

Physical activity will be assessed at V1, VPP1, and VPP2 via the International IPAQ (Physical Activity Questionnaire, long form). The IPAQ represents a well-accepted, validated instrument for monitoring population levels of physical activity in different settings and countries. It will be analysed via published guidelines for data processing and analysis at the IPAQ homepage Guidelines for data processing and analysis of the international physical activity questionnaire (IPAQ): In short, collected data will be summarized as median MET (metabolic equivalent of task) minutes per week, representing a continuous score for walking, moderate intensity activities, vigorous intensity activities and total activities, as recommended. In addition, the Pregnancy Physical Activity Questionnaire (PPAQ) will be performed to capture information on physical activity participation and sedentary behaviour during pregnancy.

#### *2.9. Assessment of maternal intramyocellular and intrahepatocellular lipids*

Intramyocellular (IMCL), and intrahepatocellular lipids (HCL) will be measured in a subgroup of 40 patients (20 rt-CGM, 20 SMBG) at V3 and after delivery (VPP2) based on previously described methods. The participants will be studied in supine position within the nuclear magnetic resonance (NMR) spectrometer. For IMCL measurements the calf muscle (right leg) will be positioned in a quadrature bird cage H volume coil. A circular H surface coil will be positioned over the liver for HCL measurement. Patients will be positioned with a left pelvic tilt to avoid pressure on the inferior vena cava according to other studies in pregnancy. Magnetic resonance measurements will be performed on a 3.0-T Siemens or Philips System. NMR spectrometry is a non-invasive technique to evaluate metabolic physiology and was shown to be safe and well tolerated by pregnant women in previous studies.

#### *2.10. Fetal biometry*

Parameters of fetal anthropometry as determined by ultrasound as well as neonatal data including length, weight, gestational age at delivery will be included in the final analysis. A detailed fetal ultrasound examination will be performed at V2 and repeated at V4 (between 36+0 to 38+6 weeks of gestation) to assess fetal growth parameters including head circumference, biparietal diameter and abdominal circumference and abdominal fat thickness,

femur length (measured and expressed as standardized gestational age related fetal growth percentiles ), amnion fluid index as well as size and location of the placenta and fetal subcutaneous tissue thickness. Moreover, fetal growth symmetry will be assessed by fetal head to abdomen circumference ratio and fetal doppler measurements (mainly umbilical artery and middle cerebral artery and ductus venosus). Furthermore, fetal hepatic size (all hepatic diameters, such as area and volume) and umbilical venous volume flow and an echocardiatic examination of the fetus will be performed in a subgroup (only study site Vienna).

### *2.11. Obstetric Outcome*

Obstetric outcome (caesarean section, birth injury, preterm birth before 37 completed weeks of gestation) stillbirth, small for gestational age (birth weight <10. Pct), large for gestational age infant (birth weight >90. Pct), shoulder dystocia, admitted to neonatal intensive care unit umbilical cord blood pH, APGAR score) will be recorded immediately after delivery. Length of hospital stay for mothers and offspring as well as duration of high-level neonatal care, respiratory distress, fetal hyperbilirubinemia and neonatal death ≤28 days will be further assessed. Calculations of age and sex adjusted percentiles will be performed by using international anthropometric standards according to those used in the CONCEPTT study. Neonatal hypoglycaemia is defined as local blood glucose ≤31 mg/dl [1.7 mmol/l] in the first 24h after delivery and ≤45 mg/dl [2.5 mmol/l] after the first 24h after delivery or treatment with glucose infusion according to the HAPO study. Additional anthropometric measures of the offspring include: head, shoulder and abdominal circumference, length, upper and lower arm and leg circumference and skin fold measurements (suprailiac and subscapular, triceps, quadriceps) in accordance with previous studies. Thereby Skinfold measurements will be performed by using a validated instrument (Harpenden Skinfold Caliper) within 48h after delivery (VPP1).

### *2.12. Assessment of cord blood*

17 ml cord-blood (1x8 ml serum and 1x9 ml EDTA) will be taken immediately after delivery to examine cord-blood glucose, insulin and C-peptide.

### *2.13. Postpartum OGTT*

The OGTT will be performed at VPP2 (i.e. 8 – 16 weeks after delivery): after collecting blood samples for measurements of glucose (2 ml blood), insulin and C-peptide (3 ml blood) in the fasting state (at least 8 hours), participating females will receive a standardized 300 ml 75g glucose. Further blood samples of glucose, insulin and C-peptide measurements will be taken at 30, 60, 90, and 120 minutes. Insulin sensitivity during the OGTT will be assessed by the oral glucose insulin sensitivity index (OGIS) according to; this quantifies dynamic glucose

clearance per unit change of insulin. The more recently developed PREDIM index will be used in addition. As an approximation for hepatic insulin resistance the homeostasis model assessment of insulin resistance (HOMA-IR) will be used. Insulin secretion will be calculated by using the C-peptide deconvolution method.  $\beta$ -cell function parameters, such as pancreatic glucose sensitivity and rate sensitivity, and potentiation of insulin secretion, will be computed through mathematical modelling.

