## Synopsis

**Introduction:** Real-time continuous glucose monitoring (rt-CGM) systems provide users with information about current interstitial glucose levels and alert the patient before the upper or lower glucose threshold is reached or when glucose levels change rapidly. Hence, glycaemic excursions can be early identified and accordingly adapted by behavioural change or pharmacologic intervention. Randomized controlled studies adequately powered to evaluate the impact of long-term application of rt-CGM systems on the risk reduction of adverse obstetric outcomes are missing.

**Study Design:** Open-label multicentre randomized controlled trial with two parallel groups including a total of 372 female patients with recent diagnosis of GDM: n=186 with rt-CGM (Dexcom G6), n=186 with self-monitored blood glucose (SMBG). Following the recommendations for the evaluation of complex interventions, a health economic evaluation will be performed.

**Visits:** Women with GDM will be consecutively recruited at their first appointment after diagnosis (V1) and randomized to either treatment (rt-CGM augmented glucose monitoring) or control group (routine care SMBG) after a run-in period of 6-8 days at the second visit (V2). The third visit (V3) will be scheduled 8 to 10 days after V2 and further follow-up visits every two weeks. At every visit glucose measurements (SMBG or rt-CGM) will be evaluated by the medical staff and all patients will be treated according to the standard of care for patients with GDM. From V2 to V3 as well as once for ten days between gestational week 36+0 and 38+6 the control group will receive blinded CGM. Cord blood will be sampled immediately after delivery (VPP0). A postpartum examination will be scheduled within 48 hours after delivery (VPP1) for assessment of neonatal biometry and maternal HbA1c, as well as **between 8 weeks to 12 months** after delivery (VPP2) in all patients for a detailed re-examination of glucose metabolism including blinded CGM for 8 to 10 days in both groups.

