#### *2.14. Assessment of health-related quality of life and patients' preferences*

Health-related quality of life will be elicited using the SF36 and the EQ-5D-5L. It can be expected that adherence to life style and dietary recommendations are associated with risk and time preferences. Hence, risk and time preferences will be elicited based on lottery approaches. Regarding risk preferences, participants will be asked to choose between two hypothetical lotteries that differ in expected outcomes which enables us to derive an individual classification of the risk type, i.e. risk-averse, risk-neutral or risk-loving. Time preferences will be elicited in a similar lottery framework whereat participants are faced with a trade-off between lower benefits now or higher benefits later on. Time preferences allow us to classify participants according to present-biased individuals and patient ones. Quality of life as well as risk and time preferences will be assessed at V1, VPP1, and VPP2. Obstetrical patient's satisfaction will be additionally assessed at VPP1 by using the Wijma score.

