#### *2.15. Health economic evaluation*

For the evaluation of a complex intervention, a health economic evaluation is recommended as well. In this study, a cost-effectiveness and a cost-utility analysis will be performed from the perspective of the health insurance. Effect measures will be avoided cases of LGA newborns as well as quality-adjusted life-years (QALYs). QALYs will be calculated using the SF36 assessment and the SF-6D that derives preference-based scores from the SF-36 by using population-based preferences (utilities) for the SF-36 health states. Intervention costs as well as health care costs (direct costs) will be calculated. For the elicitation of health care use a validated instrument will be used. Health care use will include e.g. clinical visits for the mother and associated procedures during trial and after delivery, inpatient stays, office-based visits, medication, glucose monitoring supplies and devices. Costs will be estimated and considered from the perspective of the health insurance. Since the evaluation covers only the observation period alongside the trial, costs and effects will not be discounted. Outcomes are incremental cost-effectiveness and cost-utility ratios (ICER/IUCR: additional cost per additional LGA newborn avoided or per quality-adjusted life year gained).

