newborn avoided or per quality-adjusted life year gained) will be calculated. 95% confidence intervals will be analysed using bootstrap procedures. To consider uncertainty, univariate and probabilistic sensitivity analyses will be performed and cost-acceptability curves will be created. A two-sided p-value  $\leq 0.05$  is considered statistically significant. All analyses will be performed by using the statistic software R and contributing packages. No further adjustment for multiplicity is planned for this study.

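### The postpartum visit VPP2 has two conflicting windows (8–16 weeks; 8 weeks to 12 months), and the economic analysis neither fixes an end point nor allows for unequal follow-up

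*Combined protocol and SAP*

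**What the plan says.** **The visit window.** Section 2.13 reads "The OGTT will be performed at VPP2 (i.e. 8 – 16 weeks after delivery". The synopsis has "as well as between 8 weeks to 12 months after delivery (VPP2) in all patients" and section 2.3 has "between 8 weeks and 12 months after delivery (VPP2". Section 2.3 lists the OGTT among the procedures of that visit: "as well as a blinded CGM for 10 days and an OGTT to assess the presence of prediabetic conditions after pregnancy with GDM". No section defines a separate, narrower window for the OGTT.

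**The economic evaluation.** Section 2.14 makes VPP2 the last utility measurement: "Quality of life as well as risk and time preferences will be assessed at V1, VPP1, and VPP2". Section 2.15 describes the period covered only in general terms: "Since the evaluation covers only the observation period alongside the trial, costs and effects will not be discounted". On resource use it says "Health care use will include e.g. clinical visits for the mother and associated procedures during trial and after delivery", with no closing date. Section 3.2 adds cost-effectiveness and cost-utility ratios, sensitivity analyses and the statement that "95% confidence intervals will be analysed using bootstrap procedures". It gives no horizon, no interpolation rule and no method for women followed for different lengths of time.

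**The concern.** Sites in several countries could schedule VPP2 quite differently while each follows the protocol as it reads it. Section 2.13 equates VPP2 itself with 8–16 weeks, so the conflict cannot be explained as a tighter OGTT window inside a wider visit window.

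The second issue follows from the first. A QALY is utility multiplied by time, so the period counted is part of the outcome definition. The only natural anchor for the end of that period is VPP2, whose date varies between women and is itself in dispute. If totals ran to each woman's own VPP2, part of the variation in QALYs and costs would reflect appointment dates and not health or resource use. If the rule is left open until the open-label data are in, its choice becomes discretionary.

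**Working it through.** The plan gives no economic figure to reproduce. The arm size of 169 comes from section 3.1 and does reproduce: 13.7% vs 25.8% at 169 per arm gives power 0.80 at two-sided 0.05. Utilities, standard deviations (SDs), correlations, effects and visit timing below are assumptions, because the documents give none. Twelve months is taken as 52 weeks.

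**1. Spread of follow-up.** Latest to earliest VPP2: 52/8 = 6.5 (wide window), 16/8 = 2 (narrow). Adding A antenatal weeks from V1 to delivery, (A+52)/(A+8) = 3.9, 3.3, 2.9 and (A+16)/(A+8) = 1.5, 1.4, 1.3 for A = 7, 11, 15.

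**2. SE of the QALY difference from timing alone**, if totals run to each woman's own VPP2. SE = 0.8 × SD(t)/52 × √(2/169), with √(2/169) = 0.1088.

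| VPP2 timing | SD(t), weeks | SE, QALY |
|---|---|---|
| Uniform 8–52 | 12.70 | 0.0213 |
| 80% uniform 8–16, rest uniform 16–52 | 10.16 | 0.0170 |
| 90% uniform 8–16, rest uniform 16–52 | 7.69 | 0.0129 |
| Uniform 8–16 | 2.31 | 0.0039 |

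**3. Does a common end point do better?** Week 8 serves as the test case because it is the earliest VPP2 under both windows. Assumed: mean utility 0.75, 0.70, 0.80 at V1, VPP1, VPP2 (u1, u2, u3); SD 0.12; within-woman correlation 0.5; A = 11.

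- Own-VPP2 QALY = [A(u1+u2)/2 + t(u2+u3)/2]/52.
- 8-week QALY, by linear interpolation = [A(u1+u2)/2 + 8(u2 + (u3−u2)·4/t)]/52.

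Wide-window SEs: 0.0219 for raw own-VPP2 totals, about 0.009 after linear adjustment of those totals for follow-up time, and 0.0041 for the 8-week horizon. For a gain of 0.03 from VPP1 on, the effects are 0.0205 (own VPP2) and 0.0078 (8 weeks). SE/effect is then 0.0219/0.0205 = 1.07 against 0.0041/0.0078 = 0.53, a ratio of 2.0. Only the timing of the gain changes in this table; a ratio above 1 favours the 8-week horizon.

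| Utility gain at VPP1 / VPP2 | Raw own-VPP2 vs 8 weeks | Follow-up-adjusted vs 8 weeks |
|---|---|---|
| 0.03 / 0.03 | 2.0 | 0.83 |
| 0.01 / 0.03 | 1.3 | 0.5 |
| 0 / 0.03 | 0.5 | 0.2 |
| 0.03 / 0 | 3.1 | 1.3 |

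Under the narrow window the raw ratios for the same rows are 1.15, 0.97, 0.69 and 1.40. No option is best throughout.

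**4. Adjusting QALYs for V1 utility.** SE reduction = 1 − √(1−r²), where r is the correlation of the QALY with V1 utility.

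| Accrual rule | r | Reduction |
|---|---|---|
| Raw own-VPP2, wide | 0.27 | 4% |
| Raw own-VPP2, narrow | 0.59 | 20% |
| Follow-up-adjusted, wide | 0.64 | 24% |
| Follow-up-adjusted, narrow | 0.74 | 33% |
| 8-week horizon, wide | 0.74 | 33% |
| 8-week horizon, narrow | 0.76 | 35% |

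**5. OGTT comparisons.** With a linear drift of d SDs across weeks 8–52, the SE is multiplied by √(1 + d²/12): 1.010 for d = 0.5 and 1.041 for d = 1.0, so about 1%–4%.

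The effect on costs cannot be calculated: the documents give no unit costs and no recall period for the resource-use instrument.

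**The case against.** The strongest reply is that nothing in the plan says QALYs will be summed to each woman's own VPP2 without allowance for follow-up length. That is correct, so the step 2 figures are conditional. In the worked case a simple linear adjustment for follow-up time cuts the wide-window SE from 0.0219 to about 0.009 without any common horizon.

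A reader might infer from the 2.0 ratio that an 8-week horizon should be adopted. The documents do not support that. The ratio depends on when any utility gain occurs, and section 1.2 hypothesises long-term maternal benefit, which is the setting where an early horizon does worst (ratio 0.5, or 0.2 against adjusted totals).

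It may also be said that the evaluation is secondary, that section 3.2 describes itself as only a selection of methods, and that a separate health-economic plan is an ordinary place for a horizon. This lowers the severity. It does not supply an end point, and it does not touch the window conflict.

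Finally, V1 adjustment has nothing to do with the VPP2 window. It is offered here as a separate gain from data already collected, and under raw wide-window totals that gain is only about 4%.

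**Conclusion.** The window contradiction stands on the text alone: one visit and one OGTT have two incompatible windows. The documents do not show which is intended.

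The missing economic end point is mainly missing detail. Its cost, if totals ran to each woman's own VPP2, is a timing-only SE between 0.004 and 0.021 QALY, depending on how many women are seen late and on the assumed utility of 0.8. If one window is adopted and it is the narrow one, most of this disappears.

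A reader might infer that the economic result would be biased or invalid. The documents do not support that. Bias needs VPP2 timing or attendance to differ by arm, which nothing in the plan shows; otherwise the bootstrap intervals would carry the extra variance. LGA is fixed at birth, so the primary outcome is untouched, and for cost per LGA case avoided only the cost side could be affected. OGTT comparisons lose little. Minor severity.

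**What to change.** 1. Reconcile the VPP2 window across the synopsis, section 2.3 and section 2.13. Which window applies is for the sponsor to state.
2. Before analysis, either set one sponsor-chosen postpartum end point for costs and QALYs, with the utility interpolation rule and cost cut-off, or specify adjustment for follow-up length. Vary the choice in the sensitivity analyses already planned. The calculations here do not favour week 8 or any other horizon.
3. Adjust incremental QALYs for V1 utility. V1 precedes randomisation at V2; where the run-in is omitted (section 2.2), state that the questionnaire is completed before allocation.
4. Report VPP2 timing and attendance by arm.

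The cost is protocol and health-economics wording, with no extra visits or patients. A common end point requires resource use to be dated or recorded by period, and section 2.15 does not say whether it is. An early end point would make later postpartum data secondary, and a late one needs extrapolation for women seen earlier. Linear interpolation is approximate if recovery after delivery is not linear, and linear follow-up adjustment likewise relies on its assumed form.
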